#### 11. STATISTICAL METHODS

Additional details for statistical methods will be provided in the Statistical Analysis Plan.

### 11.1. Sample Size Rationale

A sample size of 25 patients (completers) per group provides adequate precision for the estimated dosing regimen difference for relative change in SALT score from baseline at Week 24. Precision of the estimated difference is quantified by the width of the confidence intervals for the dosing regimen difference.

### 11.2. Endpoints

#### **11.2.1.** Efficacy

The primary efficacy endpoint will be relative change in SALT score for each dose regimen from baseline at Week 24.

Secondary efficacy endpoints in each dose regimen include:

- Proportion of patients achieving at least a 90%, 75%, and 50% reduction in SALT score from baseline at Weeks:
  - 4, 8, 12, 16, 20, and 24 in the Treatment Period
- Absolute Change in SALT scores from baseline at Weeks:
  - 4, 8, 12, 16, 20, and 24 in the Treatment Period
- Relative Change in SALT scores from baseline at Weeks:
  - 4, 8, 12, 16, 20 and 24 in the Treatment Period
- Change in satisfaction of hair coverage as reported by the patient

Exploratory endpoints in each dose regimen include:

- Change in patient's eyebrows as measured by the patient's Visual Analog Scale (VAS)
- Change in satisfaction of hair coverage quality as reported by patient

#### 11.2.2. Safety

Safety and tolerability of CTP-543 will be assessed by evaluating adverse event, vital signs, concomitant medications, clinical laboratories, and electrocardiogram results, as well as physical examinations.

### 11.3. Analysis Populations

The modified Intent-to-Treat (mITT) Population will include all patients who receive study drug and have at least 1 post-treatment SALT assessment. Patients will be summarized according to study drug regimen to which they were randomized. A Per Protocol Population may be defined prior to blind break if >10% of patients have clinically significant protocol deviations. The Safety Population will include all patients who receive study drug. Patients will be summarized according to study drug regimen received (i.e., as treated) should it differ from the randomized arm.

### 11.4. Analyses

For the Treatment Period, data will be summarized by dosing regimen (BID versus QD). All data for analysis will be listed by patient.

Continuous measures will be summarized descriptively (mean, standard deviation, median, minimum value, and maximum value) and categorical measures will be presented as number and percentage.

All treatment group comparisons for efficacy are for estimation purposes and no formal inferential testing will be performed.

#### 11.4.1. Disposition and Baseline Characteristics

Disposition will be summarized by randomized dosing regimen. The number and percentage of patients, who are randomized, treated, prematurely discontinued, and completers will be summarized.

Baseline characteristics will be summarized by dosing regimen for patients participating in the Treatment Period.

Medical history will be coded with the Medical Dictionary for Regulatory Activities (MedDRA) terminology. Concomitant medications will be summarized by World Health Organization Drug Dictionary Anatomical-Therapeutic-Chemical classification and preferred term.

Concomitant medications will be summarized by World Health Organization Drug Dictionary for Anatomical-Therapeutic-Chemical classification and preferred term.

#### **11.4.2.** Efficacy

For the primary efficacy endpoint and other continuous measures, the confidence interval(s) for the dosing regimen difference at Week 24 will be calculated. For categorical measures (e.g. proportion of responders), the confidence interval(s) for the dosing regimen difference at Week 24 will be calculated based on normal approximation for the binomial distribution, using the Wald continuity correction [(1/n1 + 1/n2/2]].

#### 11.4.3. Study Drug Exposure

For each patient, the number of days of exposure to CTP-543 will be summed across the Treatment Period. The total number of days on study drug will exclude dose interruptions. The total number of days of exposure to CTP-543 will be summarized with the mean, standard deviation, median, minimum, and maximum number of days on the dose. Drug compliance will also be summarized.

#### 11.4.4. Safety

All safety summaries will be descriptive with no statistical hypothesis testing and based on the Safety Population. All safety endpoints will be listed in by-patient data listings.

Adverse events will be coded using MedDRA and summarized by system organ class and preferred term. Clinically significant deteriorations in physical examination findings will be reported and summarized as adverse events.

Laboratory values will be converted to the project-defined unit of measurement, as applicable, before analysis. Abnormal, clinically significant laboratory values will be reported and summarized as adverse events.

#### **Adverse Events**

An adverse event reported after informed consent, but before the first dose of study drug (i.e., Day 1), will be considered a pre-treatment adverse event. Treatment-emergent adverse events (TEAEs) will be defined as any adverse event that occurs after administration of the first dose of study drug until Week 24 or the Early Termination Visit. The number and percentage of patients who report TEAEs will be summarized by system organ class and preferred term.

Treatment emergent adverse events will also be summarized by intensity as well as relationship to study drug.

Patients who report the same preferred term on multiple occasions will be counted once for the preferred term: under the highest severity when summarized by severity and under the closest relationship to study drug when summarized by relationship. If a patient reports multiple preferred terms for a system organ class, the patient will be counted only once for that system organ class.

The number and percentage of patients who experience TEAEs will be summarized by dosing regimen for the following:

- By system organ class and preferred term
- By severity/intensity, system organ class, and preferred term
- By relationship to study drug, system organ class, and preferred term
- Serious adverse events by system organ class and preferred term
- Serious adverse events by relationship to study drug, system organ class, and preferred term
- Adverse events resulting in discontinuation of study drug by system organ class and preferred term
- Adverse events that result in study drug dose interruption by system organ class and preferred term

By-patient listings will be provided for any deaths, serious adverse events, and adverse events leading to discontinuation of treatment.

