#### **Number of patients (planned):**

Approximately 60 patients are planned to be enrolled in the study; approximately 30 patients per treatment arm.

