### 6. STUDY OBJECTIVES

The overall objective of the study is to compare the efficacy and tolerability of a 24 mg total daily dose of CTP-543 utilizing two different dosing regimens in adult patients with chronic, moderate to severe alopecia areata.

[figure not shown]
The secondary/exploratory objectives of the study are to assess the proportion of patients achieving defined threshold reductions in SALT score, and for patients to assess their eyebrows, hair coverage and hair coverage quality.

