Patient safety will be monitored throughout the trial. The subject will be tested to ensure they do not have the Hepatitis B or C virus, thyroid function abnormalities or latent or active Tuberculosis, during the screening period. During the first 8 weeks of the Treatment Period, hematology and serum chemistry will be conducted every 2 weeks, followed by an assessment every 4 weeks thereafter through completion of the study at 24 weeks. Lipid levels will be assessed every 12 weeks throughout the Treatment Period. Significant cytopenias or other hematologic abnormalities will be managed by severity through dose interruption, or discontinuation, and signs and symptoms of infection will be closely monitored and treated promptly. Periodic skin examinations are recommended to detect non-melanoma skin cancers including basal cell, squamous cell and Merkel cell carcinoma. Patients who experience intolerable symptoms during treatment may discontinue the study at the discretion of the Investigator. Patients may withdraw consent at any time.

The Treatment Period will last 24 weeks to assess BID and QD doses, in parallel. Assessment of treatment response with SALT for efficacy will occur at 4, 8, 12, 16, 20 and 24 weeks.

Upon completion of the 24-week Treatment Period patients will be eligible to either complete treatment and exit the study following the safety follow-up visit, or roll-over into an open-label extension study.

Approximately 60 patients are planned to be enrolled in the study; approximately 30 patients per treatment arm.

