### **10.6.** Reporting Adverse Events

The Investigator must report to Sponsor or its designee all adverse events that occur during the study from the time written informed consent is given until the final study visit or early termination, regardless of their relationship to the study drug. Serious adverse events and pregnancies will be reported from the time written informed consent is given through 30 days beyond the last dose of study drug.

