13.1 Adverse Events

AEs will be coded according to the MedDRA, version 22.0.

An AE reported after informed consent, but before the first dose of study drug (i.e., Day 1), will be considered a pre-treatment adverse event.

TEAEs are defined as any AEs with onset date/time on or after the first dose of study drug. See Appendix 3 for handling of completely or partially missing dates for AEs. In the case where it is not possible to define an AE as treatment emergent or not, the AE will be classified as treatment emergent.

An overall summary table of AEs will be provided. The frequency and percentage of patients who experienced at least one AE, TEAE, TEAE by greatest relationship with study drug, TEAE by highest severity/intensity, serious TEAE, treatment-related serious TEAE, TEAE leading to study drug discontinuation, TEAE leading to study drug dose interruption, TEAE leading to study discontinuation, and TEAE leading to death will be presented.

Frequency and percentage of patients who experienced TEAE will be summarized by SOC and PT. A patient experiencing multiple TEAEs within the same SOC will be counted only once for that SOC. Similarly, a patient experiencing multiple TEAEs within the same PT will be counted only once for that PT. TEAEs will be sorted alphabetically by SOC and PT will be presented by decreasing order of total frequency within each SOC. Serious TEAEs and treatment-related serious TEAEs will be summarized similarly.

Frequency and percentage of patients who experienced TEAE will be further broken down by greatest relationship to study drug. A treatment-related AE is defined as any TEAE that is assessed by the Investigator as definitely, probably or possibly related to study drug. A not related TEAE is defined as any TEAE that is assessed by the Investigator as unlikely related or not related to the study drug. TEAE with an unknown/missing relationship to study drug will be considered as treatment related. A patient experiencing multiple TEAEs within the same SOC will be counted only once for that SOC under the greatest relationship to study drug. Similarly, a patient

	STATISTICAL ANALYSIS PLAN, Final v1.0			
Protocol Number CP543.2003	Sponsor: Concert Pharmaceuticals, Inc.			

experiencing multiple TEAEs within the same PT will be counted only once for that PT under the greatest relationship to study drug.

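### TEAEs are summarised only as crude percentages although time under observation varies by patient; if early exit or roll-over differs between regimens, the percentages are not directly comparable

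*Protocol*

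**What the plan says.** The overall objective (Protocol 6) is to "compare the efficacy and tolerability of a 24 mg total daily dose of CTP-543 utilizing two different dosing regimens", so the adverse event tables carry part of the main comparison.

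- **Measure.** Protocol 11.4.4: "The number and percentage of patients who experience TEAEs will be summarized by dosing regimen for the following", followed by breakdowns by system organ class (SOC), preferred term, severity, relationship, seriousness, discontinuation and interruption. SAP 13.1: "Frequency and percentage of patients who experienced TEAE will be summarized by SOC and PT". By default the denominator is everyone in the analysis population (SAP 6.2).
- **Collection.** Protocol 10.6 has adverse events reported "until the final study visit or early termination"; serious events run to 30 days after the last dose. Under Protocol 7.3.1 a patient who stops early has an Early Termination Visit and should return for a Safety Follow-up Visit, which the sponsor may waive case by case.
- **Window.** Protocol 11.4.4 ends the TEAE window at Week 24 or early termination. SAP 3.4 and 13.1 openly replace this with any onset on or after first dose, with no end date.
- **Numbers.** Protocol 6.3: "Approximately 60 patients are planned to be enrolled in the study; approximately 30 patients per treatment arm". Protocol 11.1: "A sample size of 25 patients (completers) per group". Withdrawals are not replaced (Protocol 7.3).

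**The concern.** A crude percentage treats every treated patient as if watched for the same length of time. Here that is not so. A patient who leaves at Week 4 without an event stays in the denominator with the same weight as one observed event-free for 24 weeks. Completers who roll over are observed to about Week 24, and completers who attend the follow-up visit to about Week 28. If the mix of these groups differs between regimens, part of any difference in TEAE percentages reflects length of observation and not tolerability. SAP 11 summarises exposure by regimen, but in a separate table that changes no TEAE percentage.

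**Working it through.** **1. The plan's own figures.** The 25 completers cannot be reproduced, because the documents give no standard deviation and no target interval width. Setting 25 against about 30 enrolled per arm gives 1 − 25/30 = 16.7%, or about 1 in 6 not completing. This is an inference from two planning figures, one of them approximate. It is not a stated dropout rate and says nothing about either regimen separately.

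**2. Observation time under the SAP definition.**

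| Patient | TEAE observation ends at about |
|---|---|
| Leaves early, follow-up waived | Early Termination Visit |
| Leaves early, follow-up attended | Safety Follow-up Visit |
| Completes and rolls over | Week 24 |
| Completes, no roll-over, follow-up attended | Week 28 |
| Completes, no roll-over, no follow-up (a category in SAP 7.1) | Week 24 |

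**3. Model for exits unrelated to adverse events.** Assumptions not in the documents: the same constant hazard in both arms; 24-week risk R; a fraction d leaving at week t; f further weeks of observation after exit (0 or 4); completers observed to Week 24.

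Crude % = (1 − d)·R + d·[1 − (1 − R)^((t+f)/24)]

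Example with R = 30%, t = 4, f = 0: the bracket is 1 − 0.7^(4/24) = 5.8%.
- 7 of 30 leave: 23/30 × 30% + 7/30 × 5.8% = 24.3%.
- 3 of 30 leave: 27/30 × 30% + 3/30 × 5.8% = 27.6%.

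| R | Exits | Exit week | Crude %, f = 0 | Gap, f = 0 | Gap, f = 4 |
|---|---|---|---|---|---|
| 30% | 5 vs 5 of 30 | 4 | 26.0 vs 26.0 | 0 | 0 |
| 30% | 7 vs 3 of 30 | 4 | 24.3 vs 27.6 | 3.2 | 2.5 |
| 30% | 7 vs 3 of 30 | 12 | 26.8 vs 28.6 | 1.8 | 1.2 |
| 40% | 25% vs 5% | 8 | 33.9 vs 38.8 | 4.9 | 3.5 |
| 40% | 30% vs 5% | 4 | 30.4 vs 38.4 | 8.0 | 6.1 |

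Gaps are percentage points, taken before rounding. The arm losing more shows the lower figure.

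**4. Exits caused by adverse events.** Take R = 30% and 3 unrelated exits at Week 4 in each arm, and add exits in one arm that each follow a TEAE.
- Comparator: (3 × 0.058 + 27 × 0.30)/30 = 27.6%.
- Two extra: (2 + 3 × 0.058 + 25 × 0.30)/30 = 32.2%.
- Four extra: (4 + 3 × 0.058 + 23 × 0.30)/30 = 36.9%.

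The last case is again 7 versus 3 exits, but the arm losing more now shows the higher any-TEAE percentage. That excess is real: with full follow-up it would be (4 + 26 × 0.30)/30 = 39.3% against 30%, the same 9.3 points. The TEAE that caused the exit stays in the numerator, so the any-TEAE row is not pulled down.

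Later events of other types are different. Whatever the reason for leaving, a patient gone at Week 4 cannot contribute one. For such an event with a 30% risk independent of the exit, 7 versus 3 exits again gives 24.3% versus 27.6%.

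**5. Scale against sampling error.** The 90% half-width for a difference at 30 per arm is 1.645 × √(2p(1 − p)/30): 19.5 points at p = 30% and 20.8 at p = 40%. Every gap in the table is smaller. Only an extreme case exceeds it: 10 versus 0 exits at Week 4 with an 80% risk gives 18.8 points against 17.0.

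**6. Does a rate remove the artefact?** For R = 30% the hazard is −ln(0.7)/24 = 0.01486 per week. With 7 exits at Week 4, expected first events are 30 × 24.35% = 7.30, over 7.30/0.01486 = 491 patient-weeks at risk. With 3 exits they are 8.27 over 557. Both give 1.49 per 100 patient-weeks. This holds by construction under constant hazard and unrelated exits; it does not test those assumptions.

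**The case against.** The strongest case is that this is a descriptive Phase 2 study of about 60 patients with no safety inference (SAP 13), and that the plan already lets a reader see unequal follow-up: exposure in days by regimen (SAP 11), discontinuation with reasons (SAP 7.1), and TEAEs leading to interruption, drug discontinuation or study discontinuation (SAP 13.1). At 30 per arm, 4.9 points is about 1.5 patients. All of that stands and limits the weight of the point. It does not remove it: those tables would reveal an imbalance without putting any TEAE percentage on a common basis, and the shift is systematic however small.

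Three stronger readings are tempting and are not supported.

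- A reader might infer that the regimen losing more patients always shows fewer adverse events, so that the tables favour the worse-tolerated regimen. Equal loss gives no between-arm bias. An intolerable adverse event is itself a withdrawal criterion (Protocol 7.3), and such patients remain in the any-TEAE numerator.
- A reader might infer that collection ends when drug stops. The Early Termination Visit, the follow-up visit, 30-day reporting of serious events and the SAP's open window all say otherwise.
- A reader might take 1 in 6 as a planned dropout rate, or 5% versus 25% to 30% as a forecast. The first is inferred, the second assumed, and nothing in the documents predicts different loss by regimen.

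**Conclusion.** The point holds conditionally. Both documents reduce TEAEs to crude percentages while observation time varies by patient, in a trial whose overall objective includes comparing tolerability. If early exit or roll-over differs between regimens, the percentages are not directly comparable. Exits unrelated to adverse events lower the percentages of the arm losing more. Exits caused by adverse events can raise its any-TEAE percentage. Later events of other types are under-counted in either case.

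The size rests on assumed risks, exit times, constant hazard and an assumed loss in each arm: about 1 to 3 points for a moderate imbalance, and about 5 to 8 for a severe one, or 3.5 to 6 with four weeks of follow-up. All are within sampling error at 30 per arm. This is an inexpensive improvement to make before unblinding, not a flaw that invalidates the safety analysis.

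**What to change.** In SAP 13.1, beside n (%), add exposure-adjusted incidence: patients with at least one event per 100 patient-weeks at risk. Time at risk runs from first dose to the first event or, if none, to the end of that patient's TEAE observation. Give it for any TEAE, Grade 3 or higher, serious, leading to interruption or discontinuation, and each SOC.

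Two rules must be added:

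1. **End of TEAE observation.** One definition applied identically to both regimens, covering roll-overs, Week 28 attenders and early leavers with and without a follow-up visit. Events counted in the rate must fall inside the same window.
2. **Partial onset dates.** State how a first event with an incomplete date enters time at risk, because SAP 6.3 limits imputed dates to deciding treatment-emergent or concomitant status and bars them from durations.

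**Cost.** This is more than one column from existing data. SAP 11 exposure runs from first to last dose, so time to first event needs a new derivation for each category. The dates involved are already recorded, and no new data are collected. The rate assumes a roughly constant hazard, so the crude percentages should stay alongside.

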### **Clinical Laboratory**

Clinical laboratory variables will be presented in 3 ways. First, change from Baseline to each scheduled assessment will be summarized descriptively. Baseline will be defined as the laboratory value obtained before the first dose of study drug on Day 1; if Day 1 values are unavailable, then values obtained at the Screening Visit will be used.

Second, treatment-emergent potentially clinically significant (PCS) laboratory values will be identified. Potentially clinically significant values are defined as those that meet Grade 3 or Grade 4 toxicity criteria from the CTCAE criteria. Treatment-emergent PCS laboratory values are those in which the baseline value is not PCS and the post-baseline value is PCS.

Third, treatment-emergent PCS laboratory values that result in dose interruption will also be identified.

The mean change from Baseline to each scheduled assessment will be summarized descriptively by dosing regimen for each clinical laboratory variable specified in this protocol.

Concert Pharmaceuticals, Inc.

The number and percentage of patients with Abnormal, clinically significant laboratory values (per Investigator judgment) and the number and percentage of patients with treatment-emergent PCS laboratory values will be summarized by dosing regimen for each clinical laboratory variable.

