- 11. Fever, inflammation, or systemic signs of illness suggestive of systemic or invasive infection within 2 weeks prior to first dose of study drug.
- 12. Abnormal levels of thyroid stimulating hormone at Screening, defined as <0.9 x the lower limit of normal (LLN) and >1.2 x the upper limit of normal (ULN).
- 13. Screening labs outside the normal range for parameters associated with potential risk for treatment under investigation. This will include but is not limited to:
  - a. Platelets  $\leq 120 \times 10^9 / L \text{ or } \geq 600 \times 10^9 / L$
  - b. Absolute neutrophil count  $\leq 1.5 \times 10^9/L$
  - c. Hemoglobin levels  $\leq 11$  g/dL for females, or hemoglobin levels  $\leq 12$ . 5 g/dL for males
- 14. Screening blood glucose levels of hemoglobin A1c ≥6.5% (48 mmol/mol).
- 15. Abnormal liver function at Screening, defined as ≥1.5 × ULN of serum alanine transaminase, serum aspartate transaminase, serum alkaline phosphatase, or total bilirubin (unless isolated Gilbert's syndrome).
- 16. Abnormal renal function (estimated glomerular filtration rate <60 mL/min/1.73 m^2 using the MDRD equation) at Screening.
- 17. Subject has positive results for hepatitis B surface antigens (HBsAg), antibodies to hepatitis B core antigens (anti-HBc), or hepatitis C virus (HCV) at Screening.
- 18. Vaccination with herpes zoster vaccine or plans to receive a live attenuated vaccine during the study and up to 6 weeks or 5 half-lives (of the study product), whichever is longer, after the last study product administration.
- 19. Positive TB test, or history of incompletely treated or untreated tuberculosis.
  - NOTE: In cases where performance of a QuantiFERON-TB Gold test is not possible, testing with a Tuberculin Skin Test (TST) may be an option after consultation with the Medical Monitor. If the TST is negative, patients can be randomized into the study, assuming they meet all other inclusion and none of the exclusion criteria. If results are equivocal, or there is reason to believe the result is a false positive, a QuantiFERON-TB Gold must be performed before a subject is eligible for randomization.
  - NOTE: Subjects with documented completed treated with latent TB are not excluded.
- 20. History of prolonged QT syndrome or a Screening QTc interval with Fridericia's correction (QTcF) > 450 msec for males or QTcF > 470 msec for females.
- 21. History of alcohol, medication, or illicit drug abuse within 1 year before the first dose of study drug.

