#### 10. ADVERSE EVENTS

#### 10.1. Definition of Adverse Event

An adverse event is any untoward medical occurrence that may appear or worsen in a patient during the course of a study. It may be a new intercurrent illness, a worsening concomitant illness, an injury, or any concomitant impairment of the patient's health, including laboratory test values, regardless of etiology. Any worsening (i.e., any clinically significant adverse change in the frequency or intensity of a pre-existing condition) should be considered an adverse event. A diagnosis or syndrome should be recorded on the adverse event page of the eCRF rather than the individual signs or symptoms of the diagnosis or syndrome. A worsening of the condition under study, alopecia areata, will not be reported as an adverse event.

All patients will be monitored for adverse events during the study. Assessments may include monitoring of the following parameters: the patient's clinical symptoms, laboratory, physical examination findings, or findings from other tests and/or procedures.

An adverse event reported after informed consent, but before the first dose of study drug (i.e., Day 1), will be considered a pretreatment adverse event and will be captured on the eCRF. Adverse events will be considered treatment-emergent if the onset is after the first dose of study drug or if an ongoing Adverse Event worsens after dosing is initiated.

Laboratory results deemed Abnormal and clinically significant by the investigator will be recorded as an adverse event in the eCRF and should be fully investigated and repeated for verification.

Regardless of severity grade, only laboratory abnormalities that fulfill a seriousness criterion need to be documented as a serious adverse event.

If a laboratory abnormality is one component of a diagnosis or syndrome, then only the diagnosis or syndrome should be recorded on the adverse event eCRF. If the abnormality was not a part of a diagnosis or syndrome, then the laboratory abnormality should be recorded as the adverse event. If possible, the laboratory abnormality should be recorded as a medical term and not simply as an abnormal laboratory result (e.g., record thrombocytopenia rather than decreased platelets).

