13.2 Clinical Laboratory

Descriptive statistics will be presented by dosing regimen at Baseline and each post-Baseline visit for data related to chemistry, hematology, and lipids tests. Change from Baseline values will also be presented at each post-Baseline visit.

Separate listings will be provided for abnormal (low or high) chemistry (including lipids) and hematology laboratory results. Clinical laboratory results that fall outside the central laboratory reference range will be interpreted by the Investigator as Abnormal, not clinically significant (NCS) or Abnormal, clinically significant (CS). Abnormal, NCS and Abnormal, CS laboratory values will be flagged in the by-subject data listings.

Additionally, treatment-emergent potentially clinically significant (PCS) laboratory values will be identified. Potentially clinically significant values are defined as those that meet Grade 3 or Grade 4 toxicity criteria from the common terminology criteria for AEs (CTCAE) criteria. Treatment-emergent PCS laboratory values are those in which the Baseline value is not PCS and the post-Baseline value is PCS. Frequency and percentage of patients with treatment-emergent PCS laboratory values at any time on treatment will be summarized by dosing regimen for each clinical laboratory variable Frequency and percentage of patients with treatment-emergent PCS laboratory values will also be summarized by dosing regimen and post-Baseline visit for each clinical laboratory variable.

Line plots of means (+/- SEM) in laboratory value over time by dosing regimen will be presented for each hematology parameter of interest (i.e., hemoglobin, absolute neutrophils count, platelets, and reticulocytes).

	STATISTICAL ANALYSIS PLAN, Final v1.0
Protocol Number CP543.2003	Sponsor: Concert Pharmaceuticals, Inc.

Separate listings of all data for chemistry, hematology, lipids, serum pregnancy, serology, and other laboratory tests will also be provided. Treatment-emergent PCS laboratory values that result in dose interruption will be identified in these listings.

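### The treatment-emergent PCS laboratory rule leaves out a worsening from Grade 3 at baseline to Grade 4 on drug, and no other planned SAP laboratory table isolates it (minor)

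*Protocol*

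**What the plan says.** Protocol 11.4.4 (Clinical Laboratory) sets the threshold: "Potentially clinically significant values are defined as those that meet Grade 3 or Grade 4 toxicity criteria from the CTCAE criteria". Treatment emergence is then a yes/no condition on that pooled category: "Treatment-emergent PCS laboratory values are those in which the baseline value is not PCS and the post-baseline value is PCS". SAP 13.2 carries it over: "Treatment-emergent PCS laboratory values are those in which the Baseline value is not PCS and the post-Baseline value is PCS". Neither document has a rule for a grade increase within PCS, and neither mentions direction.

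Three outputs use this definition:
- the count and percentage of patients by regimen at any time on treatment (SAP 13.2);
- the same count by post-baseline visit (SAP 13.2);
- the identification of treatment-emergent PCS values that led to dose interruption (Protocol 11.4.4; flagged in the SAP 13.2 listings).

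Under SAP 6.2, percentages use the whole analysis population as denominator unless otherwise indicated.

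Laboratory changes are also reported by other routes. Protocol 11.4.4 states: "Abnormal, clinically significant laboratory values will be reported and summarized as adverse events". Protocol 10.1 adds: "Any worsening (i.e., any clinically significant adverse change in the frequency or intensity of a pre-existing condition) should be considered an adverse event". The protocol also plans a by-regimen count of patients whose values the investigator judges abnormal and clinically significant. SAP 3.4 replaces that count with shift tables in three categories: low, normal and high.

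**The concern.** PCS holds two grades, and the rule asks only whether the patient was outside PCS at baseline. A move from the lower to the higher of the two grades is therefore invisible to it. A Grade 3 value on Day 1 that becomes Grade 4 on drug cannot be counted, and if it leads to a dose interruption it does not carry the treatment-emergent PCS flag. For any analyte graded both high and low, a PCS-high baseline would, on the literal wording, also block a later PCS-low value, and the reverse.

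Comparing the tolerability of the two regimens is part of the overall objective. The treatment-emergent PCS table is the planned laboratory display that is tied to toxicity grade, so it should count every on-drug worsening into Grade 3 or 4.

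**Working it through.** The documents attach no figure to this point, so there is nothing to reproduce. I checked what the rule counts, where else the event would appear, and how often it could arise.

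**1. What the rule counts.** Take grades 0 to 4 at baseline and after baseline: 5 × 5 = 25 pairs.
- Stated rule (baseline 0–2, post-baseline 3–4): 3 × 2 = 6 pairs.
- Grade-increase rule (post-baseline 3 or 4 and above baseline): 3 pairs ending at Grade 3 plus 4 ending at Grade 4 = 7 pairs.
- Difference: one pair, Grade 3 to Grade 4. Moves from Grade 0, 1 or 2 to Grade 4 are counted by both rules.

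**2. Where else a Grade 3 to 4 change would show.**
- *Adverse event tables.* It appears if the investigator judges it clinically significant and enters it as an event. Protocol 10.1 treats an event as treatment-emergent also "if an ongoing Adverse Event worsens after dosing is initiated", but SAP 13.1 uses onset on or after first dose only. Capture therefore depends on the worsening being entered as a new event. SAP 13.1 also shows life-threatening events under severe, so Grade 4 does not stand out.
- *SAP 3.4 shift tables.* The patient stays high-to-high or low-to-low. SAP 3.4 points to Section 13.2 for these tables, but 13.2 does not describe them.
- *By-visit descriptive statistics.* Every value enters, including in the minimum and maximum (SAP 6.2 and 13.2), but the patient's shift in grade is not shown.
- *Listings.* All values are listed.

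**3. Whether eligibility removes the case.** Exclusion 13 covers "Screening labs outside the normal range for parameters associated with potential risk for treatment under investigation" and names platelet, neutrophil and hemoglobin limits. Exclusions 15 and 16 cover liver tests and eGFR. These limits apply at Screening, up to 28 days before dosing, while the laboratory baseline is the Day 1 value where there is one.
- Table 5 lists 21 chemistry variables. Limits reach 5 of them (ALT, AST, alkaline phosphatase, total bilirubin, and creatinine through eGFR), which leaves 16.
- If the HbA1c limit is credited to glucose, and total bilirubin to its direct and indirect parts, 16 − 3 = 13 remain.
- The 4 lipids are first measured on Day 1.

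Not all of these need have a Grade 3 or 4 criterion; the CTCAE cut-offs are not in the documents.

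**4. Reach.** The documents give no baseline Grade 3 rate, so both inputs here are assumptions. Let p be the share of patients at Grade 3 at baseline for one variable, and q the share of those who worsen to Grade 4. With 60 patients, the expected number at Grade 3 is 60p, and the chance of at least one omitted patient is 1 − (1 − pq)^60.

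| p | Expected at baseline Grade 3 | q = 10% | q = 25% |
|---|---|---|---|
| 0.1% | 0.06 | 0.6% | 1.5% |
| 0.5% | 0.3 | 3.0% | 7.2% |
| 1% | 0.6 | 5.8% | 13.9% |
| 2% | 1.2 | 11.3% | 26.0% |

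These chances are per variable. Variables with a Screening limit should sit at or below the first row.

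**5. Size of one case.** 1/30 = 3.3 percentage points of an arm for that variable.

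**The case against.** The strongest reply is that the gap is narrow and partly covered. The rule catches 6 of the 7 worsening pairs, and the missed one is a single-grade step. A new-onset flag is a coherent choice, and the two documents agree on it. Entry limits, the investigator's discretion under exclusion 30 and the Day 1 eligibility review make a Grade 3 baseline unusual. Safety is descriptive, so no inference changes. All of this stands, and it is why the point is minor.

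A reader might infer more than the documents support:
- *That the event enters no count and the regimen comparison misses it.* Clinically significant values go into the adverse event tables by regimen, and the by-visit statistics use every value. For the same reason the PCS table is not the only between-regimen view of marked laboratory change.
- *That the rule omits the most severe change.* Grade 0, 1 or 2 to Grade 4 is a larger change, and it is counted.
- *That the rule contradicts Protocol 10.1.* The worsening clause there concerns adverse events, and the TEAE definition in Protocol 11.4.4 has no such clause. At most there is a difference in approach.

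What the reply does not remove is the gap in the laboratory tables themselves. The adverse event route needs investigator judgment and a new entry, and the SAP dropped the protocol's count of clinically significant values in favor of shifts that cannot show this change.

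**Conclusion.** The point holds as a minor definitional gap. A Grade 3 to Grade 4 worsening on drug cannot be a treatment-emergent PCS value or carry the related dose-interruption flag, while the patient remains in the denominator. On the literal wording, a PCS baseline in one direction also blocks a PCS value in the other, for any analyte graded both ways; which analytes those are cannot be checked from the documents.

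The stated rule counts 6 grade pairs where a grade-increase rule counts 7. Each omitted patient is 3.3 percentage points of a 30-patient arm. How often this happens is not known from the documents. The 0.6% to 26.0% range per variable rests wholly on assumed rates, with screened hematology, liver and renal tests at the low end. The finding does not depend on that range; it follows from the wording of the rule.

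**What to change.** In SAP 13.2, define a treatment-emergent PCS value as a post-baseline Grade 3 or Grade 4 value whose CTCAE grade is higher than the baseline grade in the same direction. Apply the same definition to the dose-interruption flag, and record the change in SAP 3.4 before database lock. SAP 3.4 already records other departures from the protocol's safety analyses. Separate rows for Grade 3 and Grade 4 would make the shift visible but are optional. While editing, add to 13.2 the description of the shift tables that 3.4 refers to.

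The cost is one extra condition in the derivation program and a documented departure from the protocol wording. No new data are needed.
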